## **Participants**

### Sample size estimation

A total of 154 participants will be enrolled at the three participating clinics. The following assumptions were used to derive this sample size:

Proportion of Placebo+MM/MC participants achieving >95% adherence = 20%

Proportion of Vivitrol+MM/MC participants achieving >95% adherence = 40%

Power=72%

Alpha level=0.05

Participants at the Nathan Smith Clinic will be 50 HIV-infected men and women who report heavy drinking, alcohol abuse or dependence. Referrals will come from within the Nathan Smith Clinic site, via local HIV care sites, website advertisements, local papers, community postings, community physicians, other patients, local mental health centers, local hospitals, and substance abuse treatment facilities.

***Inclusion criteria:*** Each subject must:

1. Be HIV-infected.
2. Currently be prescribed HAART medication.
3. Report less than 95% adherence to their HAART medication.
4. Report heavy drinking 4 or more times in the past 4 weeks, or meet current criteria for alcohol abuse or dependence. Heavy drinking is defined as 4 or more drinks for women and 5 or more drinks for men on one occasion.
5. Be at least 18 years old.
6. Be able to understand English and provide informed consent.

***Exclusion criteria:*** No subject may:

1. Be psychotic or severely psychiatrically disabled.
2. Be currently enrolled in formal treatment for alcohol (excluding self-help, e.g. Alcoholics Anonymous)
3. Have medical conditions that would preclude completing or be of harm during the course of the study.
4. Have laboratory or clinical evidence of significant liver dysfunction (alanine aminotransferase (ALT) or aspartate aminotransferase (AST) greater than 5 times the upper limit of the normal range) or cirrhosis with a Child-Pugh classification greater than A or B.
5. Have a known contraindication to NTX therapy (e.g. requiring opioid medication for pain).
6. Be pregnant, nursing or unable to use an effective method of birth control (women).
7. Patients with a positive urine opioid screen result
8. Known hypersensitivity to naltrexone, PLG (polylactide-co-glycolide, carboxymethylcellulose, or any other components of the diluent

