Randomization: Eligible participants will be randomly assigned to VIVITROL + MM/MC or placebo + MM/MC by the investigational pharmacist. All staff, other than this individual and the study biostatistician(s), will be blind to treatment allocation. Subjects will be assigned to one of the two conditions using stratified randomization. There will be 6 strata: (a) participating clinic (3) and (b) alcohol abuse/dependence (Yes/No; 2) in the randomization scheme.

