***Statistical analyses***

General considerations: Statistical procedures and models for analyzing data have been selected according to the research hypotheses being investigated and the types of data available. In general, p-values <0.05 will be considered statistically significant. When necessary, however, we will use appropriate corrections of p-values to account for multiple statistical tests. Statistical analyses will be conducted on an intention-to-treat sample using SAS Release 8.1 (SAS Institute, Inc., Cary, NC) and SPSS 14.0 (SPSS Inc., Chicago IL) statistical packages. Where appropriate, hypotheses will be tested by independent statistical analyses using Mixed Models procedure to test for significant effect of group assignment (VIVITROL vs. placebo), time, and the interaction between group assignment and time. Loss to follow-up is of concern in longitudinal analyses, particularly if loss to follow-up is differential. We plan to use established strategies (> 90% follow-up) to reduce loss to follow-up [122, 124]. A benefit of the mixed effects models approach is that subjects who do not have complete information on the outcome variable can be included, provided that missing data is missing at random.

**Specific Aim 1:** To compare the efficacy of VIVITROL +MM/MC versus placebo +MM/MC on adherence to HAART.

**Hypothesis 1:** VIVITROL +MM/MC will lead to improved adherence to HAART when compared to placebo + MM/MC.

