HAART medication adherence, specifically focusing on the proportion of patients achieving 95% or greater HAART adherence (See justification for this threshold in Section B.7.), will be evaluated using pharmacy fill/refill data on a monthly basis and self-report. For each month of the 24-week treatment period, and the 9 and 12 month follow-up periods, we will calculate the number of days of HAART medication adherence. Because HAART, the simultaneous use of  $\geq 3$  antiretroviral medications, is considered the standard of care for HIV-infected individuals, patients will be classified as adherent when their regimen medication possession ratio (MPR) (calculated as the days' supply of medication divided by the number of days between the first fill and the last refill [84]) is  $> 0.95$ , signifying greater than 95% adherence. We will also capture the MPR of all anti-retroviral medications. In prior work, we have shown that over a one year study period in VACS, the HAART MPR was 70% compared to 77% of any anti-retroviral total (Kim et al, unpublished). For patients who are on HAART but less than 95% adherent, we will determine what proportion of this group achieved greater than 95% adherence.

For primary outcome analysis, both aggregate and stratified analyses will be carried out to compare the proportion of participants in each of the two groups who achieve  $\geq 95\%$  adherence during the last four months of observation.

The probability of achieving the primary outcome will be modeled using logistic regression analysis. An unadjusted model (treatment) and models that include covariate adjustment (treatment plus other predictor variables eg depression, race, opiate receptor genetics, CD4 level, viral load level) will be executed.

In addition and, as appropriate, linear mixed effects models will be used to assess changes in adherence over the six months of observation. Models will include a fixed effect for treatment status, time as a continuous variable representing the month of observation, and the interaction between treatment and time in order to assess difference in slopes of change by treatment status. Random effects will be included to account for intra-subject correlation of repeated measures. Additional factors that may impact rate of change in adherence include time-varying covariates such as CD4 and viral load. Model fit will be assessed with analysis of residuals and other standard methods for assessing goodness-of-fit [136].

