### **Reporting to Alkermes**

Serious Adverse Events, regardless of attribution, shall be reported to Alkermes on FDA Form 3500 within 1 business day of discovery via fax or email:

Alkermes, Inc.

Attention: Alkermes Drug Safety

Dedicated Safety [contact]

Dedicated email: [[contact]](mailto:[contact])

The written report must include the opinion of the study site's PI or designated sub-investigator as to whether the event is related to the study drug. If this relationship is determined to be possibly, probably, or definitely related to study drug, evidence to support this assessment must be provided.

The PI is responsible for monitoring the data and conducting performance and safety reviews, at the specified frequency. Either the PI or the IRB have the authority to stop or modify the study. The monitoring by the IRB will occur annually at the time of re-approval. The PI will conduct data and safety review at least quarterly and at any time a serious adverse event occurs. During the review process, the PI will evaluate whether the study should continue unchanged, requires modification or amendment to continue, or should be closed to enrollment.

During the follow-up period, any patient requiring additional intervention due to significantly increased alcohol consumption or serious psychiatric/medical symptoms will receive a referral to treatment. In addition, any and all adverse events during the follow-up period will be reported to the IRB and the Project Officer at NIAAA with serious adverse events being reported within 48 hours.

We plan to comprise the Data Safety and Monitoring Board (DSMB) with experts in antiretroviral medications and addiction pharmacotherapies. The DSMB will review the progress of the study, and also conduct an interim analysis. The DSMB will monitor the occurrence and frequency of serious adverse events on a quarterly basis and review the results of the interim analysis. The interim analysis will be conducted six months after 40 subjects have been randomized to either of the treatment groups or when all of the 40 subjects in each group have completed the treatment protocol, whichever comes first. The interim analysis will evaluate whether the proportion of subjects achieving >95% adherence differs significantly (at  $p < .05$ ) by treatment condition. This interim analysis will determine whether one of the interventions is significantly inferior to the other on the primary outcome of improving HAART adherence.

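### No primary-outcome analysis is named as decisive, and neither the randomisation factors nor baseline adherence is a named covariate; secondarily, a supplementary model offers post-randomisation CD4 and viral load

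*Combined protocol and SAP*

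**What the plan says.** **Primary outcome.** Section V.4, Specific Aim 1, says that "both aggregate and stratified analyses will be carried out to compare the proportion of participants" reaching the adherence threshold in the final four months. The stratifying factor is not named. Logistic regression follows, first with treatment alone and then as "models that include covariate adjustment (treatment plus other predictor variables eg depression, race, opiate receptor genetics, CD4 level, viral load level". That list is open, and CD4 and viral load carry no time point.

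**Multiplicity.** The general considerations add: "When necessary, however, we will use appropriate corrections of p-values to account for multiple statistical tests".

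**Pointers to an unadjusted comparison.** The sample size paragraph in Section V.3 assumes two proportions, 20% and 40%. The interim rule in Section IX.3 reads: "The interim analysis will evaluate whether the proportion of subjects achieving >95% adherence differs significantly" between arms. Neither statement fixes the final analysis.

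**Baseline information available.** The Randomization paragraph states: "There will be 6 strata: (a) participating clinic (3) and (b) alcohol abuse/dependence (Yes/No; 2) in the randomization scheme". Table 1 collects pharmacy refill data at week -1. The section on baseline and in-treatment assessments sets a 30-day pill count as baseline adherence for patients who have just started HAART. Under Specific Aim 3a, the models for CD4, HIV RNA, liver tests and FIB-4 control for baseline; no such commitment is made for adherence.

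**Supplementary model.** "In addition and, as appropriate, linear mixed effects models will be used to assess changes in adherence over the six months of observation". Its committed terms are treatment, time and their interaction. Then comes: "Additional factors that may impact rate of change in adherence include time-varying covariates such as CD4 and viral load".

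**The concern.** If several analyses of one outcome are planned and none is designated, more than one result can be called the trial's answer, and the error rate is no longer that of a single 5% test. An undertaking to correct p-values where needed does not say which result decides.

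The protocol also holds a baseline value of the outcome variable and randomises within six strata, yet names neither in the primary model. Any precision they offer may go unused in a trial with a stated power of 72%.

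The secondary issue is interpretive. CD4 and HIV RNA are measured monthly after randomisation, are listed as secondary outcomes and, in the Background's own account, lie beyond adherence on the path from alcohol to HIV outcomes. A slope difference conditional on them could be read as the drug's effect on adherence, which it is not.

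**Working it through.** **1. The plan's own power.** Inputs from the sample size paragraph: 154 patients, 20% versus 40%, alpha 0.05. Assumed: 77 per arm (patients are told they have a 50% chance of active drug) and a two-sided test.

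- SE under the null = sqrt(0.3 x 0.7 x 2/77) = 0.0739. SE under the alternative = sqrt((0.16 + 0.24)/77) = 0.0721.
- Uncorrected: (0.2 - 1.96 x 0.0739)/0.0721 = 0.767, power 77.8%.
- Continuity-corrected: (0.2 - 1/77 - 1.96 x 0.0739)/0.0721 = 0.586, power 72.1%.

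The stated 72% is the corrected figure. The simulations below use likelihood-ratio tests, which carry no continuity correction, so their unadjusted power is near 79%.

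**2. Error rate if either of two models may decide.** Two independent tests would give 1 - 0.95² = 9.75%. Tests on the same data are correlated, so the true figure is lower. Simulated null trials had n = 154, a 20% or 30% response rate, with and without strata effects, and five baseline covariates each correlated 0.2 with outcome. The unadjusted or the adjusted model was significant in 6.4-8.0% of trials over 12 runs, typically 6.7%. Single tests ran at 4.2-6.2%. The interim look is not included.

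**3. Precision from strata and baseline adherence.** Assumptions, none from the documents except n, the two rates and the six strata:

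- clinics of 50/52/52, with 60% abuse/dependence;
- permuted blocks of 4 within strata;
- clinic effects of -0.3/0/+0.3 and an alcohol effect of +/-0.15 latent SD;
- 8,000 replicates.

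Power in %, nominal and then size-matched at a 30% null:

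| Baseline-outcome correlation | Unadjusted | Strata | Strata + baseline |
|---|---|---|---|
| 0, nominal | 79.7 | 81.4 | 81.4 |
| 0, size-matched | 80.3 | 80.6 | 80.0 |
| 0.3, nominal | 78.5-79.0 | 80.2-80.8 | 82.0-82.8 |
| 0.3, size-matched | 79.4-80.5 | 79.1-80.2 | 80.8-81.9 |
| 0.5, nominal | 78.6 | 80.4-80.7 | 86.3-86.4 |
| 0.5, size-matched | 78.9-79.3 | 78.9-79.3 | 84.7-85.3 |

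Once size-matched, baseline adherence is worth 1-2 points at 0.3, about 6 at 0.5 and nothing at 0. The strata alone add almost nothing.

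The range 0.3-0.5 allows for the entry criterion, "Report less than 95% adherence to their HAART medication", which narrows the spread of baseline adherence. If 60-80% of screened patients pass and self-report correlates 0.5-1 with the pharmacy measure, an unselected correlation of 0.5 becomes 0.35-0.48, and 0.7 becomes 0.54-0.68.

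**4. Two baseline measures.** At correlation 0.5, suppose new HAART starters' pill counts correlate only 0.3 with outcome. Nominal power is 85.7%, 86.6% and 85.9% with 0, 10 and 30% new starters. It is 84.3% if the pill count is uninformative in 30% (Monte Carlo error about 0.5 points).

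**5. Time-varying markers.** At a single visit, let adherence be A = beta x treatment + e with var(e) = 1, and let the marker be rho x A plus independent noise scaled so that its variance within arm is 1. Within arm, A regresses on the marker with coefficient rho, and the marker differs between arms by rho x beta. The adjusted effect is therefore beta - rho x rho x beta = beta(1 - rho²): 96%, 84% and 64% of the truth at rho = 0.2, 0.4 and 0.6. Only the marker's sign changes for viral load.

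A random-intercept model was then simulated with 154 patients over 6 months, an assumed intraclass correlation of 0.5 and a slope set for about 80% power:

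| Same-month correlation | Slope shrinkage | Power of treatment-by-time test |
|---|---|---|
| 0.3 | 5-6% | 79.8 to 78.8% |
| 0.5 | 16-17% | 78.0 to 70.0% |
| 0.7 | 38% | 80.6 to 56.8% |

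A direct drug effect on the marker changes this. At correlation 0.5, a direct effect as large as the slope difference leaves 67% of the slope if it acts in the same direction as adherence, and about 100% if it acts in the opposite direction.

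**The case against.** **The decisive analysis is nearly implied.** The outcome, the data source and the time window are fixed. The aggregate comparison and the treatment-only logistic model are the same contrast, and the sample size and interim rule point to it. The only strata that the protocol defines are the six used for randomisation. All this is fair and makes the gap one of pre-specification. It does not close the gap: no sentence says which result decides at the end, and the adjusted models are plural and open.

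**The gains are small.** This stands for the strata, and for baseline adherence at a correlation of 0.3. Leaving out a precision covariate is an inefficiency, not an error. The proposed test itself runs at 5.1-6.1%, so part of the type I inflation remains. Its six non-intercept terms, including the new-starter indicator, rest on about 46 expected responders (30% of 154). Naming the aggregate comparison as decisive would also remove the multiplicity, with no new rule.

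**The mixed-model covariates are optional.** This stands too. A reader might infer that the plan commits its efficacy analysis to post-randomisation adjustment. It does not: that model is supplementary, its committed terms exclude the markers, and the unadjusted primary comparison is untouched.

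**The direction of bias is not certain.** Coaching includes feedback on health outcomes (Section V.3), so earlier marker values may influence later adherence. The Background cites possible direct antiviral potentiation. Adjustment would still not give the total effect, but shrinkage toward zero cannot be asserted as fact.

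**Conclusion.** The point holds and is worth correcting, but it does not threaten the trial's validity. For the primary outcome, no analysis is designated as decisive, the stratifying factor is unnamed, and neither the randomisation factors nor baseline adherence is a named covariate. If either an unadjusted or an adjusted model may decide, the assumed scenarios give a type I error of roughly 6.5-8%. The precision at stake depends on an unknown correlation, as tabulated, and comes from baseline adherence rather than the strata.

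The marker-adjusted slope is secondary. It does not estimate the total effect in Hypothesis 1, but the size and even the direction of its departure rest on assumptions.

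Two further inferences would go too far. The trial is not shown to fall short of its stated power, because 72% reproduces. Nor does the plan rule out the strata or baseline adherence: its list is illustrative and would admit both.

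**What to change.** - Name one decisive analysis of at least 95% adherence over the final four months: logistic regression on treatment, clinic, alcohol abuse/dependence and baseline adherence. Take baseline adherence from the pharmacy possession ratio, or from the 30-day pill count with an indicator for new HAART starters.
- Report a standardised risk difference beside the odds ratio.
- Keep the unadjusted comparison and all other models as supportive, and state the factor used in the stratified analysis.
- Use only baseline CD4 and viral load in efficacy models, including the adjusted logistic models. Label any model with post-baseline values as mediation or exploratory.

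**Cost:** SAP wording and one rule for new starters; no new data. The downsides are a conditional odds ratio, baseline adherence measured by two methods, and a likelihood-ratio test slightly above 5% at this sample size. A simpler alternative is to make the aggregate comparison decisive, which settles the multiplicity but forgoes the precision.

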There are multiple strategies to measure adherence (See Sections B.8. and B.9.). Based on strong evidence in support of this strategy [72, 88, 89], we have chosen to examine the percentage of patients, using pharmacy fill-refill data, who achieve 95% or better adherence to their HAART treatment as our primary outcome measure of adherence [60, 117]. We will also examine adherence using self-report data collected using AIDS Clinical Trials Group (ACTG) assessment. Patients will be classified as meeting the criteria for greater than 95% adherence if they are adherent 29-30 days out of the past 30 days. We will use the Chi-Square test to compare the proportion of patients in each randomization group meeting these criteria during each month of the study. The t-test will be used to compare HAART medication adherence between the two treatment conditions based on self-report.

**Specific Aim 2:** To compare the efficacy of VIVITROL +MM/MC versus placebo +MM/MC in reducing days of heavy drinking.

**Hypothesis 2:** VIVITROL +MM/MC counseling will lead to greater reductions in the number of days of heavy drinking when compared to placebo + MM/MC.

We plan to use a standard alcohol consumption outcome, the number of days of heavy drinking (4 or more drinks per drinking occasion for women and 5 or more drinks per drinking occasion for men) in the past 30 days. This measurement was one of the outcomes

APPROVED BY THE YALE UNIVERSITY IRB 10/11/2018 VALID THROUGH 10/13/2019  

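### Self-reported adherence is tested month by month with no single treatment contrast; one prespecified repeated-measures logistic model would serve better

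*Combined protocol and SAP*

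**What the plan says.** All of this is in Section V, item 4 (Statistical Considerations) of the combined protocol and SAP.

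- **Status of self-report.** Under Specific Aim 1 the primary measure is pharmacy-refill adherence. Self-report is supportive: "We will also examine adherence using self-report data collected using AIDS Clinical Trials Group (ACTG) assessment". A patient meets the self-report criterion with 29 or 30 adherent days out of the past 30.
- **Tests assigned to it.** The investigators will "use the Chi-Square test to compare the proportion of patients in each randomization group meeting these criteria during each month of the study". A second test follows: "The t-test will be used to compare HAART medication adherence between the two treatment conditions based on self-report". No time point is given for it.
- **Significance.** The general considerations state: "In general, p-values <0.05 will be considered statistically significant". The next sentence adds: "When necessary, however, we will use appropriate corrections of p-values to account for multiple statistical tests". No method, family of tests or trigger is named, and the self-report paragraph does not refer back to it.
- **Longitudinal modelling of adherence.** Earlier under Aim 1, where appropriate, "linear mixed effects models will be used to assess changes in adherence over the six months of observation", with treatment, time, their interaction and random effects. The text does not say which adherence measure these models take.

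**The concern.** The yes/no self-report criterion is the plan's second measure of the primary construct, and it is collected repeatedly. The only analysis expressly attached to it is a string of separate monthly comparisons. With no primary month and no overall contrast, the report could draw on six or eight p-values. If the refill result were borderline, one significant month could be offered as corroboration of Hypothesis 1.

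There is also an efficiency and missing-data cost. Each chi-square test uses only the patients who have data in that month. The general considerations themselves worry about differential loss to follow-up, and give as a benefit of mixed models that patients with incomplete data can stay in the analysis. The monthly tests give up that benefit.

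**Working it through.** **Inputs**

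- Level per test: 0.05 (general considerations). Sidedness is not stated; two-sided is assumed.
- Number of tests: the self-report paragraph gives none. Table 1 schedules the ACTG questionnaire at weeks 4, 8, 12, 16, 20 and 24, which makes six monthly on-treatment looks, and at months 9 and 12, which makes eight. The broader reading has support in the Aim 1 text on adherent days, which covers "For each month of the 24-week treatment period, and the 9 and 12 month follow-up periods".
- Patients: 154 in total (sample size estimation). A 50% chance of active drug gives 77 per arm. No dropout is assumed.
- Within-person correlation between months: not in the documents, so it is varied.

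**The plan's own figure.** The documents give no familywise error for these tests. The only design figure is 72% power for 20% versus 40%. With a two-sided 0.05 test, 77 per arm and a continuity correction:

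- Numerator: 0.20 - 1/77 - 1.96 × √(2 × 0.3 × 0.7/77) = 0.20 - 0.0130 - 0.1448 = 0.0423
- Denominator: √((0.16 + 0.24)/77) = 0.0721
- Power: Φ(0.0423/0.0721) = Φ(0.586) = 72.1%

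This reproduces the stated 72%, and so supports reading 0.05 as two-sided with 77 per arm.

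**Uncorrected chance of at least one false-positive month, independent tests**

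- Six tests: 1 - 0.95^6 = 26.5%
- Eight tests: 1 - 0.95^8 = 33.7%

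**Correlated tests.** The same patients return each month. With complete data, the correlation between two monthly test statistics under no effect equals the within-person correlation of the yes/no outcome. Simulating correlated two-sided z-tests (400,000 replicates) gives:

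| Correlation | Equal between all months: 6 / 8 tests | Decaying with time, AR(1): 6 / 8 tests |
|---|---|---|
| 0.3 | 24.1% / 30.1% | 25.4% / 32.4% |
| 0.5 | 20.8% / 25.0% | 23.5% / 29.8% |
| 0.7 | 16.4% / 19.1% | 19.8% / 25.0% |
| 0.9 | 10.9% / 11.8% | 13.3% / 16.1% |

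A direct simulation of monthly Pearson chi-square tests (77 per arm, 20% or 30% adherent, 8,000 replicates, month-to-month correlation of about 0.16 to 0.64) agrees: 18-27% for six tests and 21-33% for eight. The t-test is not counted in any of these figures.

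**How the plan treats its other repeated outcomes**

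| Outcome | Planned analysis |
|---|---|
| Heavy drinking days (Aim 2) | Repeated-measures mixed model |
| CD4, HIV RNA (Aim 3) | Repeated-measures mixed model |
| Liver tests, FIB-4 (Aim 3) | Repeated-measures mixed model |
| Sexual risk behaviours (Aim 3) | Repeated-measures mixed model |
| Self-reported adherence, yes/no (Aim 1) | Separate chi-square test each month |

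**After the change.** One prespecified contrast has a 5% error rate. If treatment and treatment-by-time were both tested at 0.05, it would be 1 - 0.95² = 9.75% with independent tests, so a single contrast should be named.

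**The case against.** The case for leaving the plan alone is substantial, and several stronger readings fail against the text.

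- **A reader might infer that the plan's error rate for self-report is as high as 34%.** It is not a stated rate. The general considerations promise correction when needed, so the figures above are the risk if none is applied. What remains is that the promise names no method or family, so the decision could be made after the results are seen.
- **A reader might take roughly 20% as a floor.** It is not: a correlation of 0.7 or more brings the risk below that for six tests, and 0.9 brings it to 11-12%. The 34% end needs eight tests and independence, which is implausible for the same patients.
- **A reader might infer that Hypothesis 1 has no other between-arm test, or that adherence has no longitudinal model.** Aim 1 also plans logistic regression, unadjusted and adjusted, and linear mixed models with random effects. The opening of Aim 1 names self-report alongside refill data, so those mixed models may have been meant to cover it. The text does not say so, and a linear model does not suit a yes/no criterion.
- **A reader might infer that the chi-square tests are invalid because measures repeat.** Each compares different people in the two arms and is valid at 5% on its own. The problem is multiplicity and lost efficiency.
- **The t-test can be read as one overall comparison.** With no time point, that reading is possible but not fixed, and it does not give an effect on the 29-30 day criterion.

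It also stands that self-report is supportive and that no decision rule depends on these tests.

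**Conclusion.** The point holds as a modest improvement to a supportive analysis. The plan specifies month-by-month tests, and names no primary month, single contrast, specific correction or descriptive status for them. Without correction, the chance of at least one false-positive month is about 11-26% for six tests and 12-34% for eight, against a nominal 5%.

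These ranges assume two-sided tests, 77 per arm without dropout, and correlations from 0 to 0.9. Perfect correlation would bring the risk back to 5%. The primary refill analysis and its type I error are untouched.

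**What to change.** Make the inferential test of self-reported adherence one prespecified repeated-measures logistic mixed model for the 29-30 day criterion over the 24-week treatment period.

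- **Terms:** treatment, month, the randomisation strata (clinic and alcohol abuse/dependence), week-0 self-reported adherence and a patient random effect.
- **Baseline:** enter the week-0 value as continuous. Entry requires reported adherence below 95%, so the yes/no version will be mostly no and carry little information.
- **Result:** one treatment odds ratio over the 24 weeks. Treat any treatment-by-month term as descriptive.
- **Missing data:** a likelihood-based mixed model keeps patients with some missing months and is valid under the missing-at-random assumption that the general considerations already adopt.
- **Display:** show monthly proportions by arm descriptively, in place of the monthly chi-square tests and the t-test.

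If the monthly tests are kept, name the correction. Bonferroni would be 0.05/6 = 0.0083 for six tests or 0.05/8 = 0.00625 for eight, at a cost in power.

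The cost is SAP wording and a little programming. No new data, visits or patients are needed.
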